#### **4. Concomitant medications**

- a. Drugs which prolong QT interval, either with a known or a conditional/ possible risk to induce Torsades de Pointes (a list of drugs is given in [Appendix 4](#) of the protocol). However, in case of a life-threatening infection, in the best interest of the patient, concomitant treatment with the study drug and the relevant anti-infectious drug, though this may be included in the list given in [Appendix 4](#), can be continued with closer monitoring.
- b. Patients receiving warfarin and phenytoin that cannot be discontinued at least one week prior to start of treatment with CB-103 and for the duration of the study.
- c. Anticoagulants: Patients receiving coumarin-type anticoagulants who cannot discontinue at least one week prior to start of treatment and for the duration of the study. Low molecular weight heparin and direct oral anticoagulants are permitted.

#### **5. Demography**

- a. Patients who are pregnant or breast feeding.

#### **6. Others**

- a. Patients who are unable or unwilling to comply with all study requirements for clinical visits, examinations, tests, and procedures.

### **DURATION OF STUDY**

The study will be completed 28 days after the last patient in Part B of the study received the last treatment.

### **END OF STUDY**

The end-of-study is reached when the last patient in Part B of the study has been on study treatment for up to 12 cycles plus the safety follow-up period of 28 days after the last dose of CB-103. In case the study is stopped before any patient was treated for 12 months, the end-of-study is reached 28 days after the last patient in Part B of the study has received his/her last dose of CB-103.

## DOSE-LIMITING TOXICITY (DLT)

DLT is defined as an adverse event or abnormal laboratory value assessed as unrelated to disease progression, inter-current illness, or concomitant medications, that occurs  $\leq$  28 days following the first dose of CB-103 (Cycle 1) and that meets any of the following criteria shown in the table below.

**Note:** For T-ALL/T-LBL patients enrolled into the confirmatory cohort of Part A or expansion cohort of Part B of the study, haematological toxicity in non-responding patients, or death after progression should not be considered as DLT.

Toxicity	Any of the following criteria
Haematology	$\geq$ CTCAE grade 3 neutropenia (ANC $<$ $1.0 \times 10^9/L$ ) lasting for $\geq$ 7 days 
	$\geq$ CTCAE grade 4 neutropenia (ANC $<$ $0.5 \times 10^9/L$ ) 
	Febrile neutropenia (ANC $<$ $1.0 \times 10^9/L$ , fever $\geq$ $38.3^\circ C$ ) 
	CTCAE grade 3 thrombocytopenia (platelets $<$ $50-25 \times 10^9/L$ ) lasting for $\geq$ 7 days and/or with signs of bleeding 
	CTCAE grade 4 thrombocytopenia (platelets $<$ $25 \times 10^9/L$ ) 
	$\geq$ CTCAE grade 4 anaemia 
Cardiac	$\geq$ CTCAE grade 3
	$\geq$ CTCAE grade 3 hypertension for $>$ 14 consecutive days despite optimal anti-hypertension therapy
Renal	Serum creatinine $>$ 2 x ULN
Hepatic	$\geq$ CTCAE grade 3 total bilirubin ( $>$ 3 x ULN)
	CTCAE grade 2 total bilirubin lasting for $\geq$ 7 days.
	$\geq$ CTCAE grade 2 total bilirubin and $\geq$ CTCAE grade 2 ALT or AST
	CTCAE grade 3 ALT or AST lasting for $\geq$ 7 days
	CTCAE grade 4 ALT or AST
	Hepatic lab parameters fulfilling Hy's Law: AST/ALT 3 x ULN and concomitant 2 x ULN for bilirubin 
Pancreatic	$\geq$ CTCAE grade 3 pancreatitis
	CTCAE grade 3 asymptomatic serum lipase lasting for $\geq$ 7 days
	CTCAE grade 3 symptomatic serum lipase
	CTCAE grade 4 serum lipase
Other adverse events	Any CTCAE grade 5 toxicity
	$\geq$ CTCAE grade 3 blurred vision or any other eye disorder
	$\geq$ CTCAE grade 3 vomiting or nausea for $\geq$ 72 hours despite optimal anti-emetic therapy 
	$\geq$ CTCAE grade 3 diarrhoea for $\geq$ 72 hours despite optimal anti-diarrhoea treatment 

CONFIDENTIAL

May not be used, divulged, published, or otherwise disclosed without the consent of Cellestia Biotech AG

	Any other ≥ CTCAE grade 3 adverse event, except for the exclusions noted below
	Inability to administer CB-103 on ≥ 75% of scheduled treatment days during cycle 1 (i.e., ≥ 21 days for a 28-day daily dosing schedule) due to unresolved adverse event of any grade related to CB-103.
	Delay in 2 nd cycle administration due to failure of recovery from a possibly, probably or definitely related adverse event to grade ≤ 1 or baseline by Day 43 (D28 of cycle 1 + 15 days), except for alopecia.
Exceptions to DLT criteria	CTCAE grade 3 or 4 elevations in alkaline phosphatase
	< 96 hours of CTCAE grade 3 fatigue
	Investigations (e.g., laboratory values) CTCAE grade ≥ 3 which are judged not clinically significant by the Investigator 

Abbreviations: ALT, alanine aminotransferase; ANC, absolute neutrophil count; AST, aspartate aminotransferase; CTCAE, Common Terminology Criteria for Adverse Events; DLT, dose-limiting toxicity; PRBC, packed red blood cells; ULN, upper limit of normal.

NCI CTCAE v4.03 will be used for all grading.

 Patients may receive supportive care (e.g. use of granulocyte-colony stimulating factor [G-CSF], packed red blood cells (PRBCs), platelets) as per local institutional guidelines. However, during the DLT period it is not allowed to administer these supportive measures prophylactically.

 Patients fulfilling the criteria for Hy's law will need to be immediately discontinued from treatment

 Optimal therapy for vomiting or diarrhoea will be based on institutional guidelines and based on Section 7.4.7, with consideration of the prohibited medications listed in the protocol.

 An abnormal lab value / investigation should be deemed clinically significant (assessed by the Investigator) if either of the following conditions is met:

- The abnormality suggests a disease and/or organ toxicity that is new or has worsened from baseline
- The abnormality is of a degree that requires additional active management, e.g., change of dose, discontinuation of the drug, close observation, more frequent follow-up assessments, or further diagnostic investigation.

Therefore, a clinically significant lab value is one that indicates a new disease process, an exacerbation or worsening of an existing condition, or requires further action(s) to be taken.

During the MTD/RP2D confirmatory cohort of Part A of the study and during Part B, the study will use the CTCAE version 4.03 criteria to capture toxicities and these will be managed, and dose modified as described in Section 7.4.6. The CRC will review at least on a quarterly basis all CTCAEs ≥ grade 3, all SAEs, all clinically significant laboratory abnormalities and all available safety data to confirm the proposed dose for the expansion part is safe and well tolerated. The CRC will recommend, if necessary, to pause enrolment or implement additional safety monitoring while such a review is undertaken.

All decisions made by the CRC will be captured in meeting minutes.

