#### **Part A – Dose escalation (Phase I)**

Part A will be a dose-finding study based on a 2-parameter BLRM to investigate the safety and tolerability of sequentially enrolled dose cohorts of at least 3, up to 6 patients per dose cohort. Depending on the BLRM, additional patients may be enrolled in some dose cohorts. The first two patients of each dose level will be enrolled in a staggered approach with at least 1 day apart between first dosing of these patients. Subsequent patients may be enrolled concurrently, with at least 1 day apart from the second patient, whereby a dose cohort must be completed with regards to the DLT assessment period and be reviewed by the Cohort Review Committee (CRC) established for this study before further patients are dosed in the next dose cohort. The BLRM will be assessed for those patients satisfying the requirements for inclusion in the dose-determining set (DDS). After completion of a given dose cohort, or at any time the BLRM is updated, the decision to dose escalate and the actual dose and schedule chosen will depend on the recommendation of the BLRM about the highest admissible dose according to the EWOC principle and medical review of available clinical, pharmacokinetic and laboratory data. The outcome of these analyses and the respective datasets will be reviewed by the CRC consisting of the Investigators, Sponsor and CRO representatives, and independent functional experts as required (see Section 5.1.4.1). The CRC will make the decision to determine the next dose level and schedule for the next dose cohort.

Any dose level cohort that has been declared safe after the DLT period, may be expanded by individual patients in order to collect additional pharmacodynamic (PD) and pharmacokinetic (PK) information to support and/or confirm the mechanism of action and

explore doses at the currently tolerated dose level or below. These patients will be counted for the respective cohort at the future CRC meetings and will contribute towards the overall safety, PK, PD and clinical efficacy evaluation.

When the MTD/RP2D is defined, based on the decision of the CRC, approximately 45 additional NOTCH-positive patients with recurrent/metastatic ACC, breast cancer, r/r T-ALL/T-LBL, or any other solid tumour with proven Notch pathway activation will receive the MTD/RP2D dose to ascertain that optimal safety related to efficacy and pharmacodynamics in the tumour and in peripheral blood are achieved.

[figure not shown]

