### **5.1.4 Committees**

#### **5.1.4.1 Cohort Review Committee**

Prior to enrolment of patients into Part A (escalation) of the study, a cohort review committee (CRC) will be established, consisting of the Principal Investigators of at least those sites where the patients are enrolled, Sponsor CMO/designee and representatives, CRO representatives (e.g. medical monitor, statistician) and independent experts as required (e.g. cardiology expert). The CRC will oversee safety, cohort evaluation, dose escalation and the evaluation of MTD/RP2D for the study. A formal charter which will

establish the rules, meeting frequency and scope of responsibilities of the CRC will be prepared prior to the start of the study.

For the review of a dose level by the CRC, there will be at least 3, up to 6 patients evaluable for DLT. The CRC will review data from one complete treatment cycle (28 days) for at least 3 patients in the respective dose cohort to authorise dose escalation.

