dose that may not be exceeded at any decision point during escalation and the maximum increase in dose allowed by the protocol, intermediate doses may be administered to subsequent new cohorts of patients. This includes doses lower than the starting dose or an intermediate dose between the current and next (lower or higher) provisional dose and different schedules. To further characterise the safety (e.g. specific suspected treatment-related adverse events) or PK/PD of CB-103 a dose that is considered acceptably safe, i.e., shown to be lower than any potential MTD, may be expanded.

Dose escalation may be terminated at any time based on emerging safety concerns without establishing the MTD.

The DLT period starts from the administration of the first oral dose until 28 days after the first oral dosing (1st cycle of CB-103). Intermediate dose levels of CB-103 may be explored, e.g. in case of MTD.

During the MTD/RP2D confirmatory cohort, if in specific subgroups (e.g., by indication or ethnicity) a higher rate of toxicities occurs or the PK profile of CB-103 is different, dose adjustments in such subgroups may be decided.

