### 10.1 ANALYSIS SETS

The **safety set** will consist of all patients who received at least one dose of CB-103 and had at least one post-baseline safety assessment (where the statement that a patient had no adverse event on the Adverse Events eCRF constitutes a safety assessment). The safety set will be the primary population for all efficacy and safety related endpoints except determination of the dose-DLT relationship.

The **dose-determining set (DDS)**, which is the analysis set used for determination of the MTD, will consist of all patients in the safety set, who have (a) experienced DLT at any time during Cycle 1, and/or (b) met the minimum treatment and safety evaluation requirements without experiencing DLT within Cycle 1, as described below.

For all dose levels, from starting dose to the respective dose escalation levels, 3-6 patients will be enrolled and treated with CB-103 according to a staggered inclusion scheme to ensure adequate time for safety observation between inclusions, and before dose escalation. Depending on the BLRM, additional patients may be enrolled in some dose cohorts. The minimum treatment and safety evaluation requirements will have been met if, in Cycle 1, the patient has been treated with the planned dose of CB-103 for  $\geq 21$  days ( $\geq 75\%$  of the planned dose; minimum exposure criterion), was observed for  $\geq 28$  days following the Cycle 1 Day 1 dose, and has completed the required safety evaluations for Cycle 1. Patients who do not meet these minimum treatment and safety evaluation

requirements will be regarded as ineligible for inclusion in the DDS. Unless they experienced a DLT, patients will be replaced until the minimum number of 3 patients required for evaluation is reached.

The DDS will be used in the BLRM to estimate the dose-DLT relationship.

The **PK set** consists of all patients who have at least received one dose of study drug and have at least one post-dose PK measurement.

Patients who were screened and have signed the informed consent but did not receive any treatment will be listed including reason for screen failure and any serious adverse event that is related to study procedure. These patients will not be part of any summary table except for summarising disposition.

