#### 3.2 Dose-Determining Set

The dose-determining set (DDS), which is the analysis set used for determination of the MTD, will consist of all patients in the safety set, who have (a) experienced DLT at any time during Cycle 1, and/or (b) met the minimum treatment and safety evaluation requirements without experiencing DLT within Cycle 1, as described below.

For all dose levels, from starting dose to the respective dose escalation levels, 3-6 patients will be enrolled and treated with CB-103 according to a staggered inclusion scheme to ensure adequate time for safety observation between inclusions, and before dose escalation. Depending on the BLRM, additional patients may be enrolled in some dose cohorts. The minimum treatment and safety evaluation requirements will have been met if, in Cycle 1, the patient has been treated with the planned dose of CB-103 for  $\geq 21$  days (75% of the planned dose; minimum exposure criterion), was observed for  $\geq 28$  days following the Cycle 1 Day 1 dose, and has completed the required safety evaluations for Cycle 1. Patients who do not meet these minimum treatment and safety evaluation requirements will be regarded as ineligible for inclusion in the DDS. Unless they experienced a DLT, patients will be replaced until the minimum number of 3 patients required for evaluation is reached.

The DDS will be used in the BLRM to estimate the dose-DLT relationship.

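### A related event still holding dosing at Day 28 can become a DLT at Day 43, yet the plan lets that patient count as DLT-free when the next dose is decided

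*Protocol*

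**What the plan says.** The last DLT criterion in the synopsis table concerns a second cycle delayed by a possibly, probably or definitely related event that has not returned to grade 1 or baseline "by Day 43 (D28 of cycle 1 + 15 days"). The row above it makes missing too many Cycle 1 doses a DLT: fewer than 21 of 28 daily doses given, "due to unresolved adverse event of any grade related to CB-103".

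The timing rules for the dose decision are these:

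- **DLT period** (Protocol 7.4.3): "The DLT period starts from the administration of the first oral dose until 28 days after the first oral dosing".
- **Cohort completion** (Protocol 5.1.1): before the next cohort is dosed, "a dose cohort must be completed with regards to the DLT assessment period" and be reviewed.
- **CRC minimum** (Protocol 5.1.4.1): "The CRC will review data from one complete treatment cycle (28 days) for at least 3 patients" to authorise escalation.
- **DDS** (Protocol 10.1, SAP 3.2): a patient enters either having "experienced DLT at any time during Cycle 1", or having "met the minimum treatment and safety evaluation requirements without experiencing DLT within Cycle 1". The second route needs at least 21 days of treatment, at least 28 days of observation, "and has completed the required safety evaluations for Cycle 1".

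The replacement rules (Protocol 7.4.5, 8.11.1.1 and 10.1) cover early discontinuation and inadequate exposure. Neither document says how to count a patient whose DLT status is still open at Day 28.

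**The concern.** One DLT criterion needs 43 − 28 = 15 more days than the data on which escalation may be authorised. A patient can satisfy every condition for the DLT-free route at Day 28 while that criterion cannot yet be judged. At that decision the error runs one way: DLTs can be under-counted, never over-counted. Overdose control exists to guard against this direction. A later model update may correct the count, but possibly after the next cohort has been dosed.

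**Working it through.** **Who is exposed.** On daily dosing, a continuous hold with its first missed dose on Day *s* leaves *s* − 1 doses by Day 28.

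- *s* = 21 gives 20 doses, below 21, so it is already a DLT under the dosing criterion.
- *s* = 22 gives 21 doses, which meets the DDS minimum.

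The exposed patients therefore have a related hold starting on Day 22 or later, or interruptions totalling at most 28 − 21 = 7 days. Most events of grade 3 or higher are DLTs outright, so the exposed events are mainly of grade 2:

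- Grade 2 visual symptoms stop dosing (Protocol Table 7), while eye disorders are outright DLTs only from grade 3. Related blurred vision was reported in 12% of patients (Protocol 2.5.6), with no grades given.
- Grade 2 thrombocytopenia stops dosing (Table 4) and is not itself a DLT.
- Grade 2 bilirubin stops dosing (Table 6) but is already a DLT at 7 days or more.
- Grade 2 diarrhoea stops dosing only if uncontrolled (Table 9).

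**Model.** logit p(d) = log α + β·log(d/150), with the prior of Protocol Table 19: weights 0.5 and 0.5; means (−1.122, 0.299) and (−1.682, −0.101) for (log α, log β); SDs about 1.985 and 0.9906; correlation −0.00047. The likelihood is binomial and the posterior comes from a 1501 × 1501 grid. P(OD) = P(p(d) ≥ 0.33), and a dose is barred when this exceeds 0.25 (Protocol 10.5.1.2).

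**Reproducing Appendix 10, Table 1.**

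| Scenario | Dose (mg) | Stated P(OD) | Recomputed |
|---|---|---|---|
| 1 | 30 | 0.031 | 0.029 |
| 2 | 15 | 0.239 | 0.241 |
| 4 | 60 | 0.035 | 0.032 |
| 5 | 30 | 0.121 | 0.110 |
| 7 | 60 | 0.162 | 0.157 |
| 8 | 60 | 0.102 | 0.099 |

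All agree to within about 0.011. Scenarios 4 and 5 differ by one DLT at 30 mg, and the protocol's own next dose changes from 60 mg to 30 mg.

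**Effect of one reclassified patient.** The assumed ladder is the Table 3 doses followed by 600 and 800 mg, with the same n at every level and no DLTs at lower levels. Entries are P(OD) at the next dose; bold exceeds 0.25.

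| Step (mg) | 0 DLT, n=3 | 1 DLT, n=3 | 1 DLT, n=4 | 1 DLT, n=5 | 1 DLT, n=6 |
|---|---|---|---|---|---|
| 15→30 | 0.029 | **0.370** | **0.280** | 0.215 | 0.166 |
| 30→60 | 0.032 | **0.282** | 0.207 | 0.157 | 0.123 |
| 60→120 | 0.089 | **0.374** | **0.311** | **0.267** | 0.235 |
| 120→180 | 0.148 | **0.450** | **0.385** | **0.338** | **0.302** |
| 180→240 | 0.108 | **0.434** | **0.350** | **0.290** | 0.245 |
| 240→320 | 0.078 | **0.363** | **0.273** | 0.212 | 0.168 |
| 320→400 | 0.046 | **0.268** | 0.181 | 0.126 | 0.090 |
| 400→600 | 0.056 | **0.281** | 0.197 | 0.143 | 0.107 |
| 600→800 | 0.037 | 0.230 | 0.147 | 0.098 | 0.067 |

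A smaller step can remain admissible: 50 mg after 1/3 at 30 mg (0.228), and 90 mg after 1/3 at 60 mg (0.248).

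**Would dropping the open patient help?** With three patients it leaves two, below the minimum, so escalation waits. With four or more it does not help. At 120→180 mg the remaining DLT-free patients give 0.146, 0.129 and 0.118 for cohorts of four, five and six, so escalation proceeds as it would now.

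**The case against.** The 28-day figures are minimums, and the CRC may wait. It also reviews toxicity that is not a DLT (Protocol 10.5.1.2), so an event holding dosing at Day 28 would be in front of it. Protocol 5.1.4.1 asks for patients evaluable for DLT, and an open patient is arguably not evaluable. The charter mentioned there may settle the matter. All of this lowers the practical risk. None of it puts a rule into the DDS definition, which decides what enters the model. The cap of 50% on the next step (Protocol 7.4.3) needs related toxicity of grade 2 or higher in more than one patient, so it misses the single case.

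A reader might infer that a Day 43 DLT is lost for good. The documents do not support that. The definition ties the 28 days to when the event occurs and lists the criteria separately, and the Day 43 row could hardly operate otherwise. On that reading the patient enters the DDS as a DLT, and the cumulative update (Protocol 10.5.1.2) includes it. What remains is that Protocol 7.4.4 and 10.1 speak of DLTs in the first cycle without confirming this reading, and that the correction may come after the next dose has been given.

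The case against high priority also largely stands. The one DLT reported in 41 patients was a gamma-glutamyl transferase elevation, not a delay. Once-daily escalation had already reached 600 mg, and the next step, to 800 mg, does not cross the limit at any cohort size examined.

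**Conclusion.** The concern holds in a narrow form. Following the plan as written, a patient with a late Cycle 1 related hold can be modelled as DLT-free at the decision for which the status matters. If such a patient later proves to be a DLT, the planned next step would have been barred at every assumed step up to 400→600 mg with three per level, at five steps with four, at three with five, and at one with six. The 41 patients over eight cohorts in Protocol 2.5.6 average about five per cohort.

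These figures are conditional on such a patient occurring. They also rest on the assumed ladder, which the trial did not follow exactly: Protocol 2.5.6 mentions 250 mg and makes 600 mg cohort 8. They do not show that any dose in this trial was wrongly cleared. In this version the remaining benefit for dose decisions is mainly in the twice-daily schedule; its prior is not given, so its size cannot be computed. Nor can one conclude that no pending rule exists anywhere, because the CRC charter was not available. The change is worth making, with medium confidence.

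**What to change.** Amend Protocol 5.1.4.1, 7.4.4 and 10.1 and SAP 3.2 to state that:

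1. The 28-day limit refers to onset of the event, as the DLT definition already suggests.
2. Whatever the cohort size, when a patient has a related event unresolved at Day 28 that delays Cycle 2, the CRC either waits for recovery or Day 43 before escalating, or runs the BLRM with that patient provisionally counted as a DLT and escalates only to a dose admissible under that run. The patient is not simply dropped from the DDS.
3. A DLT confirmed by Day 43 counts as a Cycle 1 DLT, and the BLRM is rerun.

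If the CRC charter already holds such a rule, bring it into these sections. The cost is a wording change, plus an occasional delay of up to 15 days or a smaller dose step.

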## PRIMARY OUTCOME MEASURES

The primary outcome measures for this study are as follows:

Part A (Escalation):

- Dose limiting toxicities (DLT)

Part B (Expansion):

- Best overall response according to the respective tumour assessment criteria for the different cancer indications

